7.1.4.4 Calibration of Critical Equipment

The investigator or qualified designee has the responsibility to ensure that any critical device or instrument used for a clinical evaluation/test during a clinical trial that provides important information about inclusion/exclusion criteria and/or safety or efficacy parameters shall be suitably calibrated and maintained to ensure that the data obtained is reliable and/or reproducible. Documentation of equipment calibration must be retained as source documentation at the trial site.

Critical Equipment for this trial includes:

ECG machine, equipment for vital signs measurements, glucometers, Yellow Springs Instrument (YSI) glucose analyzer, GlucoScout, syringe/infusion pumps for administering glucose and study drugs, CGM, and insulin pump.

7.1.5 Visit Requirements

Visit requirements are outlined in Section 6.0 - Trial Flow Chart. Specific procedure-related details are provided above in Section 7.1 - Trial Procedures.

7.1.5.1 Screening

Within 30 days prior to Day 1 in Parts 1 – 3, or prior to Day 1 in Period 1 for Part 4, potential subjects will be evaluated to determine that they fulfill the entry requirements as set forth in Section 5.1.

Subjects may be rescreened after consultation with the Sponsor. Rescreening should include all screening procedures listed in the protocol flow chart, including consent review. Rescreen procedures cannot be conducted the day prior to treatment allocation/randomization if there are Day -1 procedures planned per protocol.

7.1.5.2 Treatment Period Visit

Subcutaneous MK-1092 (Parts 1, 2, 3, and 4) or glargine (Parts 1, 3, and 4) will be administered as a one-time injection on Day 1 of each panel or period. Intravenous Humalog (Part 2) will be infused for 3 hours starting ~12 hours after the administration of SC MK-1092 on Day 1. The actual start time of Humalog infusion was confirmed based on data from Part 1 and was communicated to the site prior to dosing for Part 2.

Exogenous glucose will also be infused concurrently with adjustments as needed to maintain a stable glucose concentration predefined by the subject's baseline fasting glucose (Parts 1 and 2), or protocol-defined target glucose (Parts 3 and 4), during the medication infusion and longer if necessary. Details of this euglycemic clamp technique are outlined in the Study Operations Manual.

7.1.5.3 Post-Trial

Subjects will be required to return to the clinic on Day 14 (+/- 2 days) in Part 1-3 or on Day 14 (+/- 2 days) of the last period dosed in Part 4 for a post-trial visit for end of trial safety assessments (e.g. physical exam, ECG, VS, lab safety tests and AE assessments) and for the assessment of anti-drug antibodies (ADA) and anti-insulin antibodies (AIA). Subjects will additionally be required to return to the clinic on Day 28 (+/- 3 days) in Parts 1-3 or on Day 28 (+/- 3 days) of the last period dosed in Part 4 for collection of samples for assessment of ADA and AIA. A follow-up phone call should be placed to the subject on Day 33 (+2 days) in Parts 1-3 or on Day 33 (+/- 2 days) of the last period dosed in Part 4 for the assessment of adverse experiences.

If a subject has a drug-induced positive ADA/AIA response at the Day 28 (+/- 3 days) visit, an additional sample will be drawn on Day 56 (+/- 5 days) in Parts 1-3 or on Day 56 (+/- 5 days) of the last period dosed in Part 4 after the completion of dosing. At the same time, fasting blood glucose will be assessed using point-of-care glucose analyzer (e.g. YSI) and an evaluation of possible signs and symptoms of hyperglycemia will be conducted. If medically required the subject will be referred to an endocrinologist for further treatment.

Additional follow-ups will be conducted in subjects with detectable ADAs until one of the following occurs:

- a) subject no longer has detectable drug-induced ADAs/AIAs,
- b) Drug-induced ADAs/AIAs are persistent and stable (magnitude of response not significantly increasing) on 3 consecutive checks at Day 28, Day 56 and additional 3 month intervals, if needed

Fasting blood glucose will be assessed by point-of-care glucose analyzer (e.g. YSI) at each time a subject returns for drug-induced ADA/AIA follow-up, and an evaluation of possible signs and symptoms of hyperglycemia will be conducted. Subjects will be referred to an endocrinologist if medically required. If a post-trial visit for the continued assessment of ADAs/AIAs occurs after Day 28 (+/- 3 days), a subsequent phone call should be made to the subject 5 (+2 days) after the last protocol-specified procedure to determine if any adverse events have occurred since the previous contact for the assessment of AEs.

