- g. All adverse experiences (including serious adverse events) will be reported from the signing of informed consent through Day 33 (5 days from Day 28 relative to the last period dosed) for randomized subjects only. If a subject is required to return for additional post-trial visits for the continued assessment of ADAs/AIAs after Day 28 (+/- 3 days), a subsequent phone call should be made to the subject 5 (+2) days after the last protocol-specified procedure to determine if any adverse events have occurred since the previous contact for the assessment of AEs. Refer to Section 7.2 for pre-randomization/allocation AE/SAE reporting requirements.
- h. Injection site local tolerability assessment will be recorded as an AE if any reactions are identified.
- i. For postmenopausal females without menses for at least 1 year.
- j. Screening UDS is mandatory, any additional UDS are conducted per site SOP
- k. This sample should be drawn for planned analysis of the association between genetic variants in DNA and drug response. This sample will not be collected at the site if there is either a local law or regulation prohibiting collection, or if the IRB/IEC does not approve the collection of the sample for these purposes. If the sample is collected, leftover extracted DNA will be stored for future biomedical research if the subject signs the FBR consent. If the planned genetic analysis is not approved, but FBR is approved and consent is given, this sample will be collected for the purpose of FBR.
- l. Leftover main study plasma will be stored for future biomedical research, if the subject consents to future biomedical research.

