7.1.4 Other Procedures

7.1.4.1 Withdrawal/Discontinuation

The investigator or trial coordinator must notify the Sponsor when a subject has been discontinued/withdrawn from the trial. If a subject discontinues for any reason at any time during the course of the trial, the subject may be asked to return to the clinic (or be contacted) for a post-trial visit (approximately 14 days after the last protocol-specified procedure) to have the applicable procedures conducted. However, the investigator may decide to perform the post-trial procedures at the time of discontinuation or as soon as possible after discontinuation. If the post-trial visit occurs prior to 14 days after the last protocol-specified procedure, the investigator should perform a follow-up phone call 14 days after the last protocol-specified procedure to determine if any adverse events have occurred since the post-trial clinic visit. An additional follow-up phone call should be made to the subject on Day 33 (+ 2 days) to determine if any adverse events have occurred since the last contact. For Parts 1 – 3, Day 33 is relative to Day 1 in each panel. In Part 4, Day 33 is relative to Day 1 of the last period dosed prior to discontinuation. Any adverse events which are present at the time of discontinuation/withdrawal should be followed in accordance with the safety requirements outlined in Section 7.2 - Assessing and Recording Adverse Events.

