or discontinuation of usual therapy, diet, placebo treatment or a procedure. From the time of treatment allocation/randomization through Day 33 (5 days after Day 28), or 5 days after the last protocol-specified procedure if additional follow-up ADA/AIA assessment visits are required, all adverse events must be reported by the investigator. For Parts 1 – 3, Day 33 is relative to Day 1 in each panel. In Part 4, Day 33 is relative to Day 1 of the last period dosed. Such events will be recorded at each examination on the Adverse Event case report forms/worksheets. The reporting timeframe for adverse events meeting any serious criteria is described in section 7.2.3.1. The investigator will make every attempt to follow all subjects with non-serious adverse events for outcome.

Electronic reporting procedures can be found in the Electronic Data Capture (EDC) data entry guidelines. Paper reporting procedures can be found in the Investigator Trial File Binder (or equivalent).

7.2.1 Definition of an Overdose for This Protocol and Reporting of Overdose to the Sponsor

The subject has taken (accidentally or intentionally) any drug administered as part of the protocol and exceeding the dose as prescribed by the protocol. It is up to the investigator or the reporting physician to decide whether a dose is to be considered an overdose, in consultation with the Sponsor.

If an adverse event(s) is associated with (“results from”) the overdose of Sponsor's product or vaccine, the adverse event(s) is reported as a serious adverse event, even if no other seriousness criteria are met.

If a dose of Sponsor's product or vaccine meeting the protocol definition of overdose is taken without any associated clinical symptoms or abnormal laboratory results, the overdose is reported as a non-serious Event of Clinical Interest (ECI), using the terminology “accidental or intentional overdose without adverse effect.”

All reports of overdose with and without an adverse event must be reported by the investigator within 24 hours to the Sponsor either by electronic media or paper. Electronic reporting procedures can be found in the EDC data entry guidelines. Paper reporting procedures can be found in the Investigator Trial File Binder (or equivalent).

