7.2.3 Immediate Reporting of Adverse Events to the Sponsor

7.2.3.1 Serious Adverse Events

A serious adverse event is any adverse event occurring at any dose or during any use of Sponsor's product that:

- Results in death;
- Is life threatening;
- Results in persistent or significant disability/incapacity;
- Results in or prolongs an existing inpatient hospitalization;
- Is a congenital anomaly/birth defect;
- Is an other important medical event.

Note: In addition to the above criteria, adverse events meeting either of the below criteria, although not serious per ICH definition, are reportable to the Sponsor in the same timeframe as SAEs to meet certain local requirements. Therefore, these events are considered serious by the Sponsor for collection purposes.

- Is a cancer;
- Is associated with an overdose.

Refer to [Table 9](#) for additional details regarding each of the above criteria.

For the time period beginning when the consent form is signed until treatment allocation/randomization, any serious adverse event, or follow up to a serious adverse event, including death due to any cause, that occurs to any subject must be reported within 24 hours to the Sponsor if it causes the subject to be excluded from the trial, or is the result of a

protocol-specified intervention, including but not limited to washout or discontinuation of usual therapy, diet, placebo treatment or a procedure.

For the time period beginning at treatment allocation/randomization through Day 33 (5 days after Day 28), or 5 days after the last protocol-specified procedure if additional follow-up ADA/AIA assessment visits are required, any serious adverse event, or follow up to a serious adverse event, including death due to any cause, whether or not related to the Sponsor's product, must be reported within 24 hours to the Sponsor either by electronic media or paper. Electronic reporting procedures can be found in the EDC data entry guidelines. Paper reporting procedures can be found in the Investigator Trial File Binder (or equivalent). For Parts 1 – 3, Day 33 is relative to Day 1 in each panel. In Part 4, Day 33 is relative to Day 1 of the last period dosed.

Additionally, any serious adverse event, considered by an investigator who is a qualified physician to be related to the Sponsor's product that is brought to the attention of the investigator at any time outside of the time period specified in the previous paragraph also must be reported immediately to the Sponsor.

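### The Part 4 closing adverse-event call (7.1.5.3) may be made on Day 31 or 32, before the Day 33 end of reporting; the other closing-call windows have no early side

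*Combined protocol and SAP*

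**What the plan says.** Section 7.1.5.3 gives two windows for the same closing call. For the first three parts: "A follow-up phone call should be placed to the subject on Day 33 (+2 days) in Parts 1-3". For Part 4 the call is placed "on Day 33 (+/- 2 days) of the last period dosed in Part 4". The same section puts the last routine Part 4 visit "on Day 28 (+/- 3 days) of the last period dosed in Part 4 for collection of samples".

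The reporting period is fixed elsewhere. Section 7.2 requires all adverse events to be reported: "From the time of treatment allocation/randomization through Day 33 (5 days after Day 28"). It adds the anchor: "In Part 4, Day 33 is relative to Day 1 of the last period dosed". Footnote g of the Part 4 flow chart (6.4) repeats the end day: "through Day 33 (5 days from Day 28 relative to the last period dosed) for randomized subjects only". Section 7.2.3.1 uses the same period for serious events: "For the time period beginning at treatment allocation/randomization through Day 33 (5 days after Day 28"). Section 7.2.3.2 does likewise for events of clinical interest.

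For subjects who discontinue, section 7.1.4.1 says: "An additional follow-up phone call should be made to the subject on Day 33 (+ 2 days"). It then states how Day 33 is counted in Part 4, so the rule covers that part. After additional antibody follow-up visits, 7.1.5.3 and footnote g of 6.4 set a further call 5 days after the last procedure, with an allowance of 2 days later and none earlier.

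**The concern.** The closing call is the last scheduled contact at which a completing subject is asked about adverse events, unless a drug-induced antibody response at Day 28 brings the subject back. If it may be made before the reporting period closes, the plan requires reports for days on which it schedules no enquiry.

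The Part 4 window also stands alone. Within Part 4, a subject who discontinues has a call window that opens on Day 33, while a subject who completes has one that opens on Day 31. The documents give no reason for the difference.

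At stake is complete collection of a primary endpoint: section 8.4 counts all types of adverse events among the primary safety endpoints. Part 4 is also the only part in which the same subjects are dosed in successive periods. For Parts 1-3, section 4.2.3.1 explains that a single MK-1092 administration was planned to limit antibody formation.

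**Working it through.** This is a count of days; no power or error-rate formula applies. Days are counted from Day 1 of the last period dosed.

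**Inputs**
- End of reporting: Day 33, described as 5 days after Day 28 (7.2; 6.4 footnote g; 7.2.3.1; 7.2.3.2).
- Part 4 closing call: Day 33 ± 2 (7.1.5.3).
- Closing call in Parts 1-3: Day 33, up to 2 days later (7.1.5.3).
- Closing call after discontinuation, Part 4 included: Day 33, up to 2 days later (7.1.4.1).
- Part 4 subjects: 9 (6 on MK-1092, 3 on glargine; sections 1.0 and 2.1).

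**Step 1. Reproduce the plan's end day.** 28 + 5 = 33, as stated.

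**Step 2. Compare the call windows with that end day.**

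| Rule | Earliest call | Latest call | Permitted call days before Day 33 | Most days left after the call, to Day 33 |
|---|---|---|---|---|
| Part 4 completers | 33 - 2 = 31 | 33 + 2 = 35 | 31, 32 | 33 - 31 = 2 |
| Parts 1-3 | 33 | 33 + 2 = 35 | none | 0 |
| Discontinued subjects, Part 4 included | 33 | 33 + 2 = 35 | none | 0 |

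**Step 3. Look for a second contact.** Neither 7.1.5.3, 7.2 nor the Part 4 flow chart asks for another call when the first is made early. The one later contact is for subjects with a drug-induced antibody response at Day 28. Their later call covers events since the previous contact, so it closes the gap for them.

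**Step 4. Upper bound across Part 4.** 9 subjects x 2 days = 18 subject-days. This requires that all nine complete, all nine are called on Day 31, and none returns for antibody follow-up. Each departure from those conditions lowers the total.

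**Step 5. Effect of a window with no early side.** The call falls on Day 33 to Day 35, and the number of reporting days after it is 0.

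**The case against.** The strongest reply is that an early call does not shorten the reporting period. Section 7.2 obliges the investigator to report all adverse events through Day 33, and 7.2.3.1 and 7.2.3.2 do the same for serious events and events of clinical interest. A related serious event that reaches the investigator is reportable at any time, and subjects carry a card with the site's telephone numbers (7.1.1.3). This stands, and it limits the point. A reader might infer that the protocol lets events on the last two days go unreported. It does not. What an early call removes is the scheduled question, so the exposure is to events that nobody volunteers, mainly non-serious or unrelated ones.

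A second reply is that 7.1.5.4 allows procedures before or after their scheduled time, so even the windows in Parts 1-3 are not an absolute bar. That is fair as far as it goes. It does not explain why the stated window has an early side only for Part 4 completers, nor does it reconcile that window with 7.2.

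A third reply is that little is likely to happen on those days. Section 4.1.2 reports geometric mean half-lives of about 5.5 to 9 hours in Part 1 (Part 4 results were pending). Day 31 is about 30 x 24 = 720 hours after dosing, or 720 / 9 = 80 half-lives at the longer value. The safety analysis is descriptive (8.6), with no incidence threshold to cross. This supports a low priority. It does not remove the conflict, because the plan itself chose Day 33 as the end of reporting.

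**Conclusion.** The inconsistency is real and small. The Part 4 call window in 7.1.5.3 opens 2 days before the reporting period in 7.2 closes, and it differs from the windows for Parts 1-3 and for discontinued subjects. At most 2 days per completing subject, and 18 subject-days in all under the conditions in the working, would have no scheduled questioning. Whether the early side is a slip or deliberate cannot be told from the documents.

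Two larger readings are tempting and should not be used:

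- **A loss of 2/33, about 6%, of post-dose adverse-event time.** A reader might infer this from the day numbers, but Day 33 is counted from the last period dosed, while reporting starts at randomization and a subject may have three periods. At the minimum 7-day spacing (2.1), the time from first dose is 7 + 7 + 33 = 47 days, and 2/47 = 4.3%. Section 1.0 gives 14-16 weeks of participation including 2-4 weeks of screening. That leaves 14 - 4 = 10 to 16 - 2 = 14 weeks (70 to 98 days), so 2/70 = 2.9% to 2/98 = 2.0%. The 6% fits only a subject dosed in a single period.
- **Five days of follow-up after the last visit reduced to none.** The Day 28 visit may be as late as 28 + 3 = Day 31, so visit and call can fall on one day. But the 5 days run from nominal Day 28, not from the actual visit, so a short gap breaches no requirement. In Parts 1-3 the gap can also be as short as 33 - 31 = 2 days.

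**What to change.** In 7.1.5.3, reconcile the Part 4 call window with 7.2 and 7.1.4.1 so that the closing call cannot precede Day 33. The wording already used for Parts 1-3, Day 33 with an allowance of 2 days later, would do this. If the early side was intended, the section should give the reason and say how events between an early call and Day 33 will be sought.

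The cost is a minor wording change. It adds no visit, telephone call or blood sample, and it leaves the reporting period and the analysis unchanged.

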7.1.5.4 Critical Procedures Based on Trial Objectives: Timing of Procedure

For this trial, the critical procedures, in order of priority, are the glucose clamp procedures followed by the blood sample collections for MK-1092 and glargine.

Blood collection and other procedures directly related to the execution of the euglycemic clamp procedure need to be completed as close to the exact timepoint as possible. In addition, at any post-dose time point, the blood sample for MK-1092 and for glargine need to be collected as close to the exact time point as possible. All other procedures should be completed as close to the prescribed/scheduled time as possible. Trial procedures can be performed prior or after the prescribed/scheduled time.

The order of priority can be changed during the trial with joint agreement of the investigator and the Sponsor Clinical Director.

Any nonscheduled procedures required for urgent evaluation of safety concerns take precedence over all routine scheduled procedures.

The following variance in procedure collection times will be permitted.

- PK Collection as outlined in [Table 8](#) below

Table 8 PK Collection Windows

| Parts 1, 2, 3 and 4 | |
|--|----------------------|
| PK collection (time post-dose in each panel or period) | PK Collection Window |
| 10 min to < 14 hr | +/- 5 min |
| 14 hr to 24 hr | +/- 10 min |
| > 24 hr to < 48 hr | +/- 30 min |
| ≥ 48 hr | +/- 2 hr |

- Predose standard safety evaluations:
 - Vital Signs: 60 min prior to dosing
 - ECG: 60 - 120 min prior to dosing
 - Laboratory safety tests & physical exam: 30 hr prior to dosing
- Postdose standard safety evaluations
 - Vital signs (up to and including 6 hrs post-dose): +/- 15 min
 - Vital signs (after 6 hrs post-dose): +/- 30 min
 - ECG, laboratory safety tests: +/- 30 min

- Pharmacodynamic or other protocol specific measurements, or modification to any of the above windows:
 - NEFA, glycerol, C-peptide, and endogenous insulin: +/- 30 min
 - ADA/AIA: +/- 6 hr

7.1.5.5 Trial Design/Dosing/Procedures Modifications Permitted within Protocol Parameters

This is a Phase I assessment of MK-1092 in humans, and the pharmacokinetic, pharmacodynamic and safety profiles of the compound is still being elucidated. This protocol is written with some flexibility to accommodate the inherent dynamic nature of Phase I clinical trials. Modifications to the dose, dosing regimen and/or clinical or laboratory procedures currently outlined below may be required to achieve the scientific goals of the trial objectives and/or to ensure appropriate safety monitoring of the trial subjects.

As such, some alterations from the currently outlined dose and/or dosing regimen may be permitted based on newly available data, but the maximum daily dose may not exceed those currently outlined in the protocol.

- Repeat of or decrease in the dose of the trial drug administered in any given period/panel
- Interchange of doses between panels or periods
- Entire period(s) or panel(s) may be omitted
- Decrease in the duration of trial drug administration (e.g., number of hours)
- Remove a planned pharmacokinetic pause if agreed by Sponsor and investigator if no further increases in total daily dose
- Addition of pharmacokinetic pause
- Addition of operational pause
- Decrease in the target glycemic level to be maintained during glucose infusion/clamp procedure
- Decrease in the number of PK sampling timepoints
- Modification of the PK/PD sample processing and shipping details based on newly available data

The pharmacokinetic/pharmacodynamic sampling scheme currently outlined in the protocol may be modified during the trial based on newly available pharmacokinetic or pharmacodynamic data (e.g., to obtain data closer to the time of peak plasma concentrations). If indicated, these collected samples may also be assayed in an exploratory manner for metabolites and/or additional pharmacodynamic markers.

Up to additional 50 mL of blood may be drawn for safety, pharmacokinetic, and/or pharmacodynamic analyses in Parts 1 – 3. Up to an additional 100 mL of blood may be drawn for safety, pharmacokinetic, and/or pharmacodynamic analyses in Part 4. This

includes additional blood that may be required for Yellow Springs Instrument (YSI) blood glucose assessments during the clamp procedure for safety. The total blood volume withdrawn from any single subject will not exceed the maximum allowable volume during his/her participation in the entire trial (Section 12.3).

The timing of procedures for assessment of safety procedures (e.g., vital signs, ECG, safety laboratory tests, etc.) currently outlined in the protocol may be modified during the trial based on newly available safety, tolerability, pharmacokinetic or pharmacodynamic data (e.g., to obtain data closer to the time of peak plasma concentrations). Additional laboratory safety tests may be added to blood samples previously drawn to obtain additional safety information (e.g., adding creatinine kinase to serum chemistry panel that was already drawn. These changes will not increase the number of trial procedures for a given subject during his/her participation in the entire trial.

It is understood that the current trial may employ some or none of the alterations described above. Any alteration made to this protocol to meet the trial objectives must be detailed by the Sponsor in a letter to the Trial File and forwarded to the investigator for retention. The letter may be forwarded to the IRB/IEC at the discretion of the investigator.

